ECOG	Eastern Cooperative Oncology Group
ESAS	Edmonton Symptom Assessment Scale
ESLD	End Stage Liver Disease
FACT-Hep	Functional Assessment of Cancer Therapy – Hepatobiliary
FAMCARE-P	Family Satisfaction with Care
FCS	Fully Conditional Specification
ICC	Intraclass Correlation Coefficient
ITT	Intention to Treat
MAR	Missing at Random
MCID	Minimal Clinically Important Difference
MELD	Model for End Stage Liver Disease
MI	Multiple Imputations
mitT	Modified Intention to Treat
PCORI	Patient Centered Outcomes Research Institute
RCT	Randomized Controlled Trial
PC	Palliative Care
PHQ-9	Personal Health Questionnaire
PROMIS-29	Patient Reported Outcomes Measurement Information System
SAP	Statistical Analysis Plan

SD	Standard Deviation
SOP	Standard Operations Procedures
QOL	Quality of Life
VA	Veterans Affairs
ZBI-12	Zarit Burden Interview

1 PURPOSE

This statistical analysis plan (SAP) briefly overviews the study design and objectives, outlines the types of analyses and data presentations that address study objectives. The SAP describes, in detail, the statistical methods for efficacy analyses specified in the study protocol (Protocol titled “Title: Introducing Palliative Care (PC) within the Treatment of End Stage Liver Disease (ESLD): A Cluster Randomized Controlled Trial”, Version 4.0). Duke Clinical Research Institute (DCRI) will conduct all statistical analyses described in this SAP.

2 STUDY OVERVIEW

This section summarizes the study objectives and design as background for the statistical methods presented in the SAP. For definitive details of the study objectives and design, consult the study protocol. Each participating patient/caregiver dyad (caregiver if available) will participate for 3 months of study intervention, and 9 months of follow up for a total of 12-months of study participation. Survival data will be collected for 12 months of participation. All patient-caregiver dyads will receive the intervention at the initial visit, and at 1, 2, and 3 months from the initial visit. Initial/ first visit will occur within 6 weeks after informed consent. All study visits can occur in person, or remotely (by phone or telehealth with the institutional secure platform). Ascertainment of baseline assessments will occur within 1 week before the scheduled in person initial visit. 1, 2 and 3 month visits can occur within a window period of 1 week (before/after) of their respective times from the initial visit. All caregiver visits can occur in person or by phone, as preferred by the caregivers. The initial caregiver visit can occur on the same day or within 1 week of patient’s initial visit. Study follow up data collection will be conducted at 6, 9 and 12

months, by phone, paper or online, within 1 week (before/after) of the due date. Originally, we planned to enroll 1260 patients, but the trial sample size was modified to enrollment of 936 patients at 19 participating sites.

2.1 Study Design

This is a two-armed cluster randomized controlled trial (RCT). Randomization occurred at the level of clinical centers, and was stratified by VA (Veterans Affairs) vs non-VA. Each arm had initially 7 clinical centers.

Clinical centers are randomized to one of two models of palliative care (PC) delivery: Model 1- Consultative PC (i.e., PC offered by a board-certified or board-eligible PC provider) or Model 2- Trained hepatologist led PC (i.e., PC offered by a trained hepatologist). An additional 5 centers were randomized (resulting in one in Model 1 and four in Model 2) and the study utilized 19 centers. Standardized protocols (including visit agenda) were be followed at each of the clinical centers to maintain intervention fidelity across sites in both models. For additional details, please refer to the study protocol.

2.2 Study Objectives

The primary objective of the PAL-LIVER study is to assess the comparative effectiveness of two PC delivery models for patients with ESLD in improving the disease specific quality of life from baseline to 3 months as assessed using FACT-Hep (Functional Assessment of Cancer Therapy- Hepatobiliary). The primary superiority hypothesis is that compared to consultative PC, ESLD patients receiving trained hepatologist led PC will have higher QOL (Quality of Life) change scores at 3 months after baseline. The superiority hypothesis will be assessed first and only if such superiority is not demonstrated (i.e., when superiority p-value > 0.05) then a non-inferiority (NI) analysis of the trained hepatologist led PC (Model 2) will be performed. The NI margin is pre-specified as Δ = 4. If the lower limit of the two-sided 95% Confidence Interval (CI) of the estimated treatment effect (Model 2 minus Model 1) is above negative Δ , then the non-inferiority of Model 2 will be demonstrated.

The secondary objectives are:

1) To compare the effects of the two above-mentioned models of PC delivery (as a change from baseline to 3 months) on:

- Overall quality of Life, assessed using PROMIS-29 (Patient Reported Outcomes Measurement Information System);
- Patient's symptom burden, assessed using modified ESAS (Edmonton Symptom Assessment Scale);
- Patient's depression severity, as assessed by PHQ-9 (Personal Health Questionnaire);
- Patient distress, as assessed by Distress Thermometer (DT) ;
- Patient satisfaction with care, assessed using FAMCARE-P13 (Family Satisfaction with Care);
- Caregiver burden, assessed by Zarit Burden Interview (ZBI-12);
- Caregiver quality of life, assessed using PROMIS-29;
- Goal concordant care measures assessed using advance directive and advance care planning documentation, a survey questionnaire and qualitative interviews with patients and caregivers.

2) To compare the effects of the two above models of PC delivery on:

- Healthcare utilization from the time of initial visit (30 and 90-day scheduled and unscheduled hospital admission rate, unscheduled office visits within 1 year, ER visits within 1 year).

3) Conduct semi structured interviews to explore and compare patient, caregiver, and provider experiences with the two models.

- Qualitative interviews of patients' and caregivers' experiences with receiving PC as a part of routine care provided by hepatologists versus palliative care providers;
- Qualitative interviews of palliative care and hepatology providers' experiences and confidence with providing PC to ESLD population.

4) The exploratory objective is to compare the effects of the two comparative models on survival over 1 year. We will use the date of informed consent as the first day in the trial.

2.3 Sample Size Determination and Statistical Power

2.3.1. Sample Size Determination

Patient-reported quality of life, as measured by FACT-Hep total score, is the primary outcome measure in this study. Published estimates show the average performance on this measure for typical patients with ESLD is 143.0 points (SD 20.6) and a difference of 9 points on this measure reflects a minimal clinically meaningful difference (MCID) in QOL [1,2]. However, the power estimates below are based on SD=19.1 for change in FACT-Hep total score from baseline to 3 months observed in the study at the time of sample size re-computation (**n=936**). Patient level data analysis will be considered with adjustment for clustering, i.e., adjustment for correlation of patients' outcomes within a cluster (site). This correlation is quantified by the intraclass correlation coefficient (ICC). At the time of sample size re-computation ICC=0.09 was noted in the study.

2.3.2. Statistical Power for Superiority Hypothesis

Power for superiority hypothesis is **83.2%** and it is based on the final enrollment in the sites and estimated (as of September 25, 2024) counts of patients evaluable for change in FACT-Hep total score from baseline to 3 months.

Power was derived via simulations utilizing multivariate normal distribution with the earlier mentioned SD=19.1 and ICC= 0.09. Each simulation consists of generating, for each of the 19 sites, the evaluable patient count of realizations from this distribution. Since only difference in means between the two arms matters, for simplicity, the consultative PC sites were considered to have zero mean and the Hepatologist led PC sites to have mean equal to MCID=9. For each simulation a mixed model $\text{change}_{ij} = \alpha + \beta \text{trt}_{ij} + s_j + e_{ij}$ was fit to the simulated data (with $\text{trt}=1$ for Hepatologist led PC-Model 2 and $\text{trt}=0$ for Consultative PC-Model 1) where response change_{ij} is change in FACT-Hep total score from baseline to 3 months for the i -th patient in the j -th site ($j=1,2,\dots,K=19$). Random effects $s_j \sim N(0, \sigma_s^2)$ inducing correlation within sites are assumed to be independent across the sites and also independent from independent random

errors $e_{ij} \sim N(0, \sigma_e^2)$. Proportion (out of 100,000 simulations) of treatment variable p-values less than 0.05 provided estimate of the power for superiority.

2.3.3. Statistical Power for Non-inferiority Hypothesis

Note that “non-inferiority” means that the true mean FACT-Hep total score change (CHANGE_H) for the Hepatologist led PC is allowed to be less than the true mean FACT-Hep total score change (CHANGE_C) for the Consultative PC, but by not more than the so-called NI margin (DELTA). Namely, we hope to reject null hypothesis $H_0: \text{CHANGE}_H \leq \text{CHANGE}_C - \text{DELTA}$ in favor of alternative hypothesis $H_1: \text{CHANGE}_H > \text{CHANGE}_C - \text{DELTA}$ (or equivalently $H_1: \beta = \text{CHANGE}_H - \text{CHANGE}_C > -\text{DELTA}$). This is accomplished by first computing a lower two-sided 95% confidence limit for β . Subsequently, if this limit is above negative DELTA, then non-inferiority (with NI margin DELTA) of the Hepatologist led PC as compared to the Consultative PC is declared. The NI margin is pre-specified at DELTA = 4.

Power for non-inferiority (NI) of Model 2 (Hepatologist led PC) is **79.2%** and was obtained via simulations as outlined above although for the NI power computations we assumed that Hepatologist led PC performs better than the Consultative PC only by half of MCID=9 (i.e., 4.5) specified in superiority hypothesis. For each simulation, the lower two-sided 95% CI limit (L) for β was computed. Proportion (out of 100,000 simulations) with $L > -\text{DELTA}$ provided power for non-inferiority of Model 2 (Hepatologist led PC).

2.4 Analysis Populations

There are two analysis populations defined for this protocol:

1. ITT (Intention to Treat) population including all randomized patients.
2. mITT (modified Intention to Treat) population is as ITT population with the exception that patients who undergo liver transplantation or hospice transfer prior to the 3 month end point are excluded. The reason for consideration of the mITT population is that the

primary quality of life FACT-Hep total score outcome is measured at 3 months and liver transplant is a curative treatment and patients in hospice undergo a much more intensive palliative care. The mITT population will be utilized in the primary analysis.

2.5 Study Endpoints

2.5.1 Primary Efficacy Endpoint

Change in quality of life from baseline to 3 months, as assessed by FACT-Hep total score (3 month score minus baseline score) in the mITT population. Total score is calculated from the FACT-Hep eCRF values according to the FACIT scoring guidelines version 4 (www.facit.org). A detailed model with adjustment for the baseline FACT-Hep total score and Veterans Affairs status will be discussed later in the document (section 5.1).

3.5.2 Secondary Efficacy Endpoints

The endpoints inset below will be assessed as a change from baseline to 3 months (3-month score minus baseline score) in the mITT population:

- Overall quality of life (PROMIS-29, separate T scores)
- Symptom burden (modified ESAS, point score for each item, potentially total score for ESAS-r (9 components) and total score for the 13 components from this study)
- Depression severity (PHQ-9, total score)
- Distress (Distress Thermometer, total score)
- Satisfaction with care (FAMCARE-P, total score)
- Caregiver burden (ZBI-12, total score)
- Caregiver quality of life (PROMIS-29, separate T scores)
- Goal concordant care (Patient and Caregiver Questionnaire, total score)

Healthcare utilization in the mITT population:

- Proportion of patients with at least one scheduled or unscheduled hospital admissions within 30 days from the initial visit (based on data available from 1 month visit).
- Proportion of patients with at least one scheduled or unscheduled hospital admissions within 90 days from the initial visit (based on data available from 3 months visit).
- Rate of ER visits within 1 year from the initial visit.
- Rate of unscheduled office visits within 1 year from the initial visit.

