## Protocol Version 4.0

2. The patient and caregiver will be provided with contact cards, available to share with other care-providers.
3. Caregivers will be asked to contact the coordinator or investigator in the event of visit to the Emergency Room or inpatient hospital stay.

**Ad hoc Palliative Care Consultation:** Hepatologists randomized to the hepatology led PC arm will have the opportunity to consult with a Palliative Care Provider. If such consultation is needed, a phone interaction will be encouraged. The ad hoc interaction between the hepatologist and the local Palliative Care Provider will be captured in the study CRF. Future intervention visits will continue, as per the schedule.

**Hospice Transfer:** In the event of a patient being admitted to home or inpatient hospice within 3 months from enrollment, the PC intervention will be stopped. However, data collection will continue as scheduled either in person during an office visit or over the phone, for both patients and caregivers until the 12 month follow up.

**Patient Transplant:** In the event of a patient undergoing liver transplantation prior to reaching the three month point, the PC intervention will be stopped. However, data collection will continue as scheduled, for both patients and caregivers until the 12-month follow-up.

**Primary Analysis Population:** Patients who undergo transplantation or hospice transfer prior to 3-month end point will not be included in the primary outcome analysis. Should they be transplanted or transferred to hospice after 3 months from enrollment, they will be included in the primary analysis.

**Scheduled hospital admission:** non-acute admission for any procedure or planned care.

**Unscheduled office visits and hospital admissions (encounters).** An unscheduled encounter will be defined as one which occurs for acute illness or complications for which care was never planned before.

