## 11.3 Statistical Analysis Plan

General Approach Statistical analysis will be performed by the Data Coordinating Center (DCC) at the DCRI. Although the methodological approaches and operational details of the data analysis will be coordinated by the study biostatisticians, the major analyses of the study data will be highly collaborative, involving both statisticians and clinicians to ensure appropriate approaches and interpretation of the data. All major treatment comparisons between the randomized groups in this trial will be performed according to the principle of "**intention-to-treat**;" that is, subjects will be analyzed (and outcomes attributed) according to the treatment group to which patients were randomized, regardless of subsequent medical care or potential discontinuation of treatment. However, patients who undergo transplantation or hospice transfer prior to the 3-month end point will not be included in the primary outcome analysis. Statistical comparisons will be performed using two-sided significance tests. Additional perspective regarding the interpretation of the data will be provided through extensive use of confidence intervals and graphical displays. Analyses will be performed with the SAS version 9.4 and R statistical software.

Baseline Demographic and Clinical Assessments including relevant descriptors from the history and baseline examination will be summarized for the two arms of the study. Descriptive summaries of the distribution of continuous baseline variables will be presented in terms of means and percentiles (median, 25th and 75th percentiles), while discrete variables will be summarized in terms of frequencies and percentages. Since randomization is expected to produce balance at baseline between the two arms of the trial, statistical comparisons of treatment groups with respect to baseline characteristics will be more informal (no statistical tests will be used) and limited to selected variables and disease factors known to influence prognosis.

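### The four healthcare-utilisation endpoints are analysed in mITT, so patients with a transplant or hospice transfer before 3 months are dropped along with utilisation already observed

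*SAP*

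**What the plan says.** SAP section 2.4 defines two populations. One is the "ITT (Intention to Treat) population including all randomized patients". The other, mITT, is the same except that "patients who undergo liver transplantation or hospice transfer prior to the 3 month end point are excluded". The reason given is that the "primary quality of life FACT-Hep total score outcome is measured at 3 months and liver transplant is a curative treatment", and that hospice patients receive much more intensive palliative care. Section 2.4 then assigns mITT to the primary analysis.

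SAP section 3.5.2 extends this to "Healthcare utilization in the mITT population" and lists four endpoints: the proportions admitted within 30 and within 90 days, and the 1-year rates of ER visits and unscheduled office visits. The 30-day endpoint concerns "hospital admissions within 30 days from the initial visit (based on data available from 1 month visit"); the ER endpoint is the "Rate of ER visits within 1 year from the initial visit". Section 5.4 gives the models (random-effects logistic regression; Poisson regression by GEE) but names no ITT version and no sensitivity analysis for utilisation.

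Protocol section 11.3 says: "All major treatment comparisons between the randomized groups in this trial will be performed according to the principle of" intention-to-treat, with one exception: patients with a transplant or hospice transfer before the 3-month end point are left out of the primary outcome analysis. Protocol section 6 (Primary Analysis Population) states the exclusion with the same scope. For transplanted patients section 6 adds that "data collection will continue as scheduled, for both patients and caregivers until the 12-month follow-up", and it makes the same provision after hospice transfer.

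**The concern.** The exclusion was built for a questionnaire score read at month 3. Admissions, ER visits and office visits accrue from the initial visit, and those before the transplant or transfer are fully observed. Removing the whole patient discards them from numerator and denominator because of something that happened afterwards.

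That later event is not clearly independent of the arm. Protocol section 4 states that proactive palliative care consultation has improved transplant rates. Goals-of-care discussion and advance directives are core content of the intervention (protocol section 6), so an effect on hospice transfer is plausible. The two arms deliver palliative care through different providers, and the protocol hypothesises lower utilisation in Model 2 (section 5.3). If the models lead to different numbers of early transplants or transfers, or if the excluded patients' utilisation differs by arm, the mITT comparison loses the protection of randomisation: a difference can be hidden or created.

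**Working it through.** **1. Scope of the exclusion.** The protocol's two statements cover only the primary outcome analysis. Section 11.3 also says that secondary outcomes summarised by a score follow the primary analysis, but admission proportions and visit rates are not scores. For these four endpoints the protocol therefore implies intention-to-treat, and SAP 3.5.2 departs from it without giving a reason.

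**2. What mITT removes, by endpoint.**
- 30-day admission: a patient transferred to hospice on day 60 has a complete window, yet leaves the analysis.
- 90-day admission: for the same patient, days 1-60 are valid observation; only days 61-90 follow the event.
- 1-year rates: a patient transplanted in month 2 contributes nothing; one transplanted in month 4 contributes in full.

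**3. Are the data available?** Collection continues to month 12 after either event (protocol section 6). Utilisation is scheduled at every time point (Table 2) and drawn from medical records and patient history (section 9).

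**4. Size.** The documents give no admission rate and no exclusion rate, so there is no stated figure to reproduce. Every rate below is an assumption.

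*Case A: admission risk in each group is the same in both arms, but the share excluded differs.* Let h be the share excluded per arm, p_ex the 30-day admission risk in those excluded and p_ot the risk in the others.
- ITT proportion = h × p_ex + (1 − h) × p_ot; mITT proportion = p_ot.
- Example with h = 10% (Model 1) vs 5% (Model 2), p_ex = 50%, p_ot = 20%: ITT gives 0.10 × 0.50 + 0.90 × 0.20 = 23.0% vs 0.05 × 0.50 + 0.95 × 0.20 = 21.5%, a difference of 1.5 points. mITT gives 20% vs 20%, a difference of 0.
- In general the gap is (h1 − h2) × (p_ex − p_ot). With exclusions from 6% vs 3% up to 10% vs 5%, p_ex of 50-60% and p_ot of 20-25%:
  - smallest: 0.03 × (0.50 − 0.25) = 0.75 points
  - largest: 0.05 × (0.60 − 0.20) = 2.0 points

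*Case B: no true ITT difference.* Let p be the 90-day admission proportion, equal in both arms, e the share excluded and p_e the risk among those excluded. Then mITT proportion = (p − e × p_e) / (1 − e). Take e = 5% vs 10%.
- p = 40%, p_e = 70%: (0.40 − 0.035)/0.95 = 38.4% vs (0.40 − 0.07)/0.90 = 36.7%, a spurious 1.8 points before rounding the two rates.
- p = 30%, p_e = 90%: (0.30 − 0.045)/0.95 = 26.8% vs (0.30 − 0.09)/0.90 = 23.3%, a spurious 3.5 points.
- With 5% excluded in both arms and the same p_e, the arm difference stays 0, but e × p_e / p = 9% to 15% of admitted patients are still dropped.

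**5. Scale.** Excluding 5% or 10% of 936 patients removes about 47 or 94. If the 936 are spread equally over 8 vs 11 sites (394 vs 542), the standard error of the Case A difference is √(0.23 × 0.77/394 + 0.215 × 0.785/542) ≈ 2.8 points before allowing for clustering. A 1.5-point shift is about half of that.

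**The case against.** **The clinical reasons may carry over.** Section 2.4 also says that transplant is curative and that hospice is a more intensive form of palliative care, and the study intervention stops at either event. Utilisation afterwards reflects different care. Scheduled admissions count, so under ITT a transplant stay within the window would itself be an admission. This stands as an argument about post-event use in the 90-day and 1-year endpoints. It does not justify deleting pre-event use, and it has no bearing on a 30-day window that closed before the event.

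**ITT is not the only answer.** This is fair. SAP section 5.5 already keeps ITT patients in the longitudinal FACT-Hep analysis and sets scores to missing after the event. Counting utilisation up to the event would follow the same logic, and the fix includes it.

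**Few patients may be affected.** Eligibility excludes those likely to be transplanted within 3 months and those with a life expectancy under 6 months, which should reduce the number. SAP section 3 reports the count. Reporting reveals the exclusions but does not correct the estimate.

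**Stronger readings that the documents do not support.** A reader might infer that everyone who ever reaches transplant or hospice is removed; only events before the 3-month end point have that effect. A reader might also infer that the excluded patients are the heaviest users of hospital care, or that hospice transfer is known to differ between the models; the documents give no data on either. Both arms deliver palliative care, so a difference in exclusions is possible but not established.

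**Conclusion.** The concern holds for all four endpoints and is clearest for 30-day admission. The SAP applies to utilisation an exclusion that the protocol reserves for the primary outcome, and it gives no reason specific to utilisation. The excluding event occurs after baseline and may be influenced by treatment.

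Bias in the arm comparison requires that exclusions, or the utilisation of those excluded, differ by arm. Its direction and size cannot be known from the documents. Under the Case A assumptions the ITT and mITT differences diverge by about 0.75 to 2.0 points; under Case B mITT shows a difference where ITT has none. The illustrated shift in 30-day admission is small against sampling error, so the calculation does not show that a conclusion would change. These are secondary endpoints: the change should be made, but the primary result does not depend on it.

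**What to change.** In SAP sections 3.5.2 and 5.4:
- Make ITT, defined as all enrolled patients by site assignment, the main population for the four utilisation endpoints.
- For the 1-year rates, use person-time to death, loss to follow-up or end of study.
- Add a sensitivity analysis that counts utilisation only up to transplant or hospice transfer.
- Show the 90-day admission and 1-year results with and without the index transplant stay (section 5.4 also models 1-year admission counts, where such a stay would enter).
- Keep mITT as a supportive analysis, and report by arm how many patients it excludes.

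The cost is SAP wording and a few extra tables; the data are already scheduled for collection. The downside is that ITT brings transplant stays and post-event care into the counts, which the sensitivity and supportive analyses make visible.
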